3.8 CRITERIA FOR REMOVAL FROM PROTOCOL THERAPY AND OFF-STUDY CRITERIA

Prior to removal from study, effort must be made to have all subjects complete an evaluation safety visit approximately 30 days following the first follow-up evaluation (at the second follow-up evaluation).

3.8.1 Criteria for Removal from Protocol Therapy

Patients will be taken off treatment for the following:

- Completion of second follow-up evaluation
- Grade 3 or 4 toxicity due to the vaccine, excluding those known events such as local injection site reactions, skin rash, pruritus, fatigue, fever and local adenopathy.
- Progression of disease
- Patient requests to be withdrawn from protocol therapy
- Investigator discretion
- Positive pregnancy test

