3.1.4 Dose-Limiting Toxicity

The dose-limiting toxicity (DLT) evaluation period for determination of the maximum tolerated vaccine dose (MTD) will occur during the 21 days after the first vaccination for each patient. A DLT is defined as follows: All grade 3 or greater toxicities related to the mRNA vaccine, with the exception of:

- Grade 3 fever
- Grade 3 pruritus/itching
- Grade 3 fatigue
- Grade 3 metabolic laboratory abnormalities without significant clinical sequela that resolve to grade 2 or less within 7 days.
- Grade 3 autoimmune toxicity that resolves to grade 2 or less within 7 days.
- Events that are clearly related to the patient's disease.
- 3.1.5 Phase I Dose Escalation

Subjects will receive their assigned dose level of NCI-4650 as IM injections on Days 0, 14, 28, and 42. The maximum dose of mRNA vaccine for each dose level will be:

Dose Level	vel NCI-4650, mRNA Vaccine Dose	
Level 1	0.04 mg (0.0006 mg/kg based on a 70-kg subject)	
Level 2	0.13 mg (0.0019 mg/kg based on a 70-kg subject)	
Level 3	0.39 mg (0.0056 mg/kg based on a 70-kg subject)	

Moderna is the sponsor of a dose escalation trial utilizing a nearly identical vaccine (mRNA-4157) as the mRNA vaccine used in this protocol (NCI-4650). The dose escalation in both protocols is the same (0.04 mg, 0.13 mg, and 0.39 mg). As indicated in the Moderna Safety Review Committee Dose Level Approval Form dated 21 December 2017, the Moderna Medical Monitor noted that for the three patients enrolled on Dose Level 1 (Part A) in the Moderna trial (0.04 mg mRNA-4157 monotherapy), no DLTs were experienced and the only AEs experienced were grade 1 injection site soreness, which is expected for the vaccine. As a result, Dose Level 1 was declared safe and tolerated. For this trial, because Dose Level 1 was shown to be safe and tolerated, the first two patients were enrolled on Dose Level 2. No DLTs were experienced and the only AEs experienced were grade 1 and 2 related events.

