3.2 PROTOCOL STOPPING RULES

New subject enrollment to the protocol will be temporarily halted if any of the following conditions are met, and consideration will be given to the need for protocol revisions regarding safety, if applicable. Consultation with the FDA may be arranged by the Sponsor before or after the protocol amendment is submitted to the NIH Intramural IRB, as needed.

- During the Phase I portion of the study If two DLTs, as described in Section **3.1.4**, occur at Dose Level 1.
- During the Phase II portion of the study Once five or more patients have been enrolled, if 20% or more patients cumulatively enrolled develop a DLT, as described in Section 3.1.4.
- During the Phase I and II portions of the study Any death that is at least possibly attributed to the investigational agent and which occurs within 30 days of receiving the investigational agent.

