3.8.2 Off-Study Criteria

Patients will be taken off-study for the following:

- Vaccine does not meet CoA requirements
- Completion of study follow-up period
- Progression of disease
- Patients begins a new therapy for their cancer
- Patient requests to be withdrawn from the study
- Significant noncompliance
- Investigator discretion
- Patient lost to follow-up
- Patients who require the use of any medications listed in Section 4 for clinical management.
- Death

All patients will be co-enrolled on protocol 09-C-0161. Patients who are taken off-study for progressive disease or study closure on the treatment protocol will be followed on protocol 09-C-0161.

Once a subject is taken off-study, no further data can be collected on this treatment protocol.

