4 CONCOMITANT MEDICATIONS/MEASURES

Use of all medications taken at any time from consent to the last safety follow-up visit must be recorded in the subject's electronic case report form (eCRF). This will include all prescription drugs, herbal products, vitamins, minerals, and over-the-counter (OTC) medications. Any changes in concomitant medications also will be recorded in the subject's eCRF.

Any concomitant medication deemed necessary for the welfare of the subject during the study may be given at the discretion of the investigator, including palliative radiation. Blood transfusions are allowed at any time during the study, except to meet eligibility criteria.

- Antineoplastic systemic chemotherapy or biological therapy is prohibited.
- Systemic corticosteroids are prohibited for any purpose other than to treat symptoms from an event of clinical interest of suspected immunologic etiology. The use of physiologic doses of corticosteroids may be approved after consultation with the investigator. If in the interest of safety, the investigator must treat the subject immediately.
- Inhaled or topical steroids, and adrenal replacement steroid doses ≤ 10 mg daily prednisone equivalent, are permitted in the absence of active autoimmune disease.
- Subjects already taking erythropoietin at the time of screening for the study may continue, provided they have been taking it for more than one month at the time study treatment is started. Prophylactic erythropoietin should not be started during screening or the first two weeks of study treatment but may be started thereafter.
- Granulocyte colony stimulating factors should not be used prophylactically during the first two weeks of study treatment. Use of prophylactic colony stimulating factors may be considered thereafter following discussion with the investigator.
- Live vaccines within 30 days prior to the first dose of NCI-4650 and while participating in the study are prohibited. Examples of live vaccines include but are not limited to the following: measles, mumps, rubella, chicken pox, yellow fever, rabies, Bacillus Calmette-Guérin, and typhoid (oral) vaccine. Seasonal influenza vaccines for injection are generally killed virus vaccines and are allowed. However, intranasal influenza vaccines (e.g., FluMist[®]) are live attenuated vaccines, and are prohibited.

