- Radiation therapy to a symptomatic solitary lesion or to the brain may be considered on an exceptional case-by-case basis after documented consultation with the investigator. The subject must have clear measurable disease outside the radiated field. Administration of palliative radiation therapy will be considered clinical progression.

Subjects who, in the assessment by the investigator, require the use of any of the aforementioned treatments for clinical management should be removed from the trial. Subjects may receive other medications that the investigator deems to be medically necessary.

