7.6 DATA AND SAFETY MONITORING PLAN

7.6.1 Principal Investigator/Research Team

The clinical research team will meet on a weekly basis when patients are being actively treated on the trial to discuss each patient. Decisions about enrollment and dose escalation, if applicable, will be made based on the toxicity data from prior patients.

All data will be collected in a timely manner and reviewed by the PI or AI. Adverse events will be reported as required above. Any safety concerns, new information that might affect either the ethical and/or scientific conduct of the trial, or protocol deviations will be reported to the NIH Intramural IRB using iRIS.

The PI will review AE and response data on each patient to ensure safety and data accuracy. The PI will personally conduct or supervise the investigation and provide appropriate delegation of responsibilities to other members of the research staff.

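### The removal rule in 3.8.1 exempts known vaccine reactions without a grade limit, so a grade 4 event of an exempt type does not require the patient to stop

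*Combined protocol and SAP*

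**What the plan says.** Section 3.8.1 lists the reasons for taking a patient off treatment. The toxicity bullet reads "Grade 3 or 4 toxicity due to the vaccine, excluding those known events such as local injection site reactions, skin rash, pruritus, fatigue, fever" and closes with local adenopathy. The same list includes investigator discretion and the patient's own request.

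Section 3.1.4 defines a dose-limiting toxicity (DLT) as "All grade 3 or greater toxicities related to the mRNA vaccine, with the exception of" a set of listed items. The entries for fever, pruritus and fatigue are each confined to grade 3. Injection site reactions, skin rash and local adenopathy have no entry of their own.

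Section 3.2 acts on accrual. In Phase II the condition is "Once five or more patients have been enrolled, if 20% or more patients cumulatively enrolled develop a DLT"; the consequence is a temporary halt to new enrolment, with consideration of safety revisions to the protocol.

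Section 6.4 adopts CTCAE v5.0 for grading and does not reproduce it. Section 1.2.9 expects mild to moderate reactions.

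**The concern.** A removal rule is the written floor under clinical judgement: it fixes the severity at which dosing ends whoever is treating the patient. Here the exemption qualifies the whole phrase covering grades 3 and 4, so on its plain reading it reaches grade 4. Tolerating grade 3 fever or fatigue after a vaccine is an understandable choice. Nothing in the text explains extending the same tolerance to grade 4, and 3.1.4 shows that the authors wrote a grade 3 limit where they wanted one.

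The result is an odd ordering. A vaccine-related grade 3 event outside the list must end treatment; a grade 4 event inside it need not. What is at stake is the further dosing of an individual patient. The response hypothesis, error rates and sample size are not involved.

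**Working it through.** No figure in the plan needs reproducing. The check sets two rules side by side, searches for any other rule that would stop the patient, and calculates how many doses could follow.

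**1. Vaccine-related events by type and grade**

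| Event type | Grade | DLT under 3.1.4, if in its evaluation period | Removal required by 3.8.1 |
|---|---|---|---|
| Fever, pruritus, fatigue | 3 | No | No |
| Fever, pruritus, fatigue | 4 | Yes | No |
| Injection site reaction, skin rash, local adenopathy | 3 | Yes, unless a rash qualifies as an autoimmune event resolving within 7 days | No |
| Injection site reaction, skin rash, local adenopathy | 4 | Yes | No |
| Types outside the 3.8.1 list | 3 | Yes, unless covered by another 3.1.4 exception | Yes |
| Types outside the 3.8.1 list | 4 | Yes | Yes |

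The grade 4 rows hold only for terms that have a grade 4 in CTCAE v5.0. The documents do not show which of the six named terms do. Because the list is illustrative, other terms could fall under it as well.

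**2. Search for another grade-based rule that stops the patient**

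- 3.1.5 uses DLTs to set cohort size and dose level.
- 3.2 halts new enrolment. In Phase II one DLT among five patients is 1/5 = 20%, which meets the threshold, but the rule says nothing about further doses for the affected patient.
- 3.3 has no rule for holding or discontinuing doses.
- 3.5.1 requires a toxicity assessment, physical examination and laboratory tests within 2 days before each later vaccination. It names no result that bars the dose.
- 3.8.2 takes off study "Patients who require the use of any medications listed in Section 4 for clinical management", and Section 4 says that patients who "require the use of any of the aforementioned treatments for clinical management should be removed from the trial". This depends on medication, not grade, and Section 4 also states that "Systemic corticosteroids are prohibited for any purpose other than to treat symptoms from an event of clinical interest of suspected immunologic etiology". A steroid course for a suspected immune reaction is therefore permitted and would not clearly trigger removal.
- 7.3 requires immediate reporting of serious adverse events to the sponsor.
- 7.6.1 provides that "The clinical research team will meet on a weekly basis when patients are being actively treated on the trial to discuss each patient".

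None of these sets a grade at which the individual must stop.

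**3. Upper limit on further dosing**

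Inputs: four vaccinations per course and at most two courses (3.1.3); 0.39 mg at Dose Level 3 (3.1.5). Take an event after dose 1.

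- One course: 4 − 1 = 3 doses; 3 × 0.39 mg = 1.17 mg.
- Two courses: 8 − 1 = 7 doses; 7 × 0.39 mg = 2.73 mg.

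Both figures assume that every remaining dose is given despite the event. The second also needs the optional second course, which 3.1.3 makes conditional on a 3-fold rise in pre-existing neoantigen-specific T-cells or on new reactivity. These are ceilings, not expected exposures.

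**The case against.** The strongest reply is that the DLT definition is the wrong yardstick. DLTs decide dose level, the maximum tolerated dose and enrolment; no section says that a DLT ends an individual's treatment. Grade 3 injection site reactions, rash and adenopathy can also be DLTs without mandatory removal, and a grade 4 limit leaves that difference in place. This stands. A reader might infer that 3.8.1 is meant to mirror 3.1.4 and fails to; the documents do not support that. Section 3.1.4 serves here only to show that the authors limit similar exceptions to grade 3.

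A reader might also infer that the gap opens when the DLT period closes, since 3.1.4 says that evaluation "will occur during the 21 days after the first vaccination for each patient". That does not follow either: no DLT rule stops the individual patient within that period, so the position is the same throughout treatment.

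The safeguards are real. Each later dose follows a clinical check (3.5.1), the team reviews patients weekly, and a grade 4 event that meets the seriousness criteria in 7.1.5 goes promptly to the sponsor. Many clinicians would stop such a patient anyway. This lowers the practical risk, but continuation still turns on judgement.

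Finally, no listed term is shown to have a grade 4, and no frequency can be given. That limits the weight of the point without changing what the bullet says. Leaving a quickly resolving event to the investigator is a defensible choice in refractory metastatic cancer; if that is the intent, the protocol should say so.

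**Conclusion.** The point holds as a narrow patient-safety wording gap. As written, 3.8.1 does not require a patient to stop after a vaccine-related grade 4 event of an exempt type, and no other section supplies a grade-based stop. Three things limit its weight: the terms concerned must have a grade 4 in CTCAE v5.0, the protocol expects mild to moderate reactions, and several non-binding safeguards exist. The documents give no grade 4 rate, so no frequency is estimated; the only figures are the dosing ceilings of 1.17 mg and 2.73 mg.

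A reader might conclude that the protocol lets patients with grade 4 toxicity be re-dosed unchecked. The documents do not support that, given the assessment before each dose and the investigator's power to stop. The supportable conclusion is that stopping is discretionary where a fixed rule would be expected. Low priority, and cheap to correct.

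**What to change.** Split the 3.8.1 toxicity bullet in two: remove the patient for any grade 4 toxicity due to the vaccine; or for grade 3 toxicity due to the vaccine, other than the known events already listed. The list keeps its present members and stays illustrative. This deliberately leaves the sponsor's tolerance of grade 3 reactogenicity alone and does not attempt to match removal to the DLT definition.

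The cost is one wording change by amendment, with no added visits or tests. The team loses the option of continuing after a grade 4 event that resolves quickly. A patient stopped before completing the first course may be inevaluable for response under 8.3.2 and, in Phase II, would then use one of the 2 inevaluable places per cohort (21 + 2 = 23 per cohort; 2 × 23 = 46, as in 8.2). The intention-to-treat analysis in 8.4.5 would still include that patient.

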3.8.2 Off-Study Criteria

Patients will be taken off-study for the following:

- Vaccine does not meet CoA requirements
- Completion of study follow-up period
- Progression of disease
- Patients begins a new therapy for their cancer
- Patient requests to be withdrawn from the study
- Significant noncompliance
- Investigator discretion
- Patient lost to follow-up
- Patients who require the use of any medications listed in Section 4 for clinical management.
- Death

All patients will be co-enrolled on protocol 09-C-0161. Patients who are taken off-study for progressive disease or study closure on the treatment protocol will be followed on protocol 09-C-0161.

Once a subject is taken off-study, no further data can be collected on this treatment protocol.

3.8.3 Off Protocol Therapy and Off-Study Procedure

Authorized staff must notify the NCI-CRO when a subject is taken off protocol therapy and when a subject is taken off-study. A Participant Status Update Form from the website

(http://home.ccr.cancer.gov/intra/eligibility/welcome.htm) main page must be completed and sent via encrypted email to the NCI-CRO at [contact].

4 CONCOMITANT MEDICATIONS/MEASURES

Use of all medications taken at any time from consent to the last safety follow-up visit must be recorded in the subject's electronic case report form (eCRF). This will include all prescription drugs, herbal products, vitamins, minerals, and over-the-counter (OTC) medications. Any changes in concomitant medications also will be recorded in the subject's eCRF.

Any concomitant medication deemed necessary for the welfare of the subject during the study may be given at the discretion of the investigator, including palliative radiation. Blood transfusions are allowed at any time during the study, except to meet eligibility criteria.

- Antineoplastic systemic chemotherapy or biological therapy is prohibited.
- Systemic corticosteroids are prohibited for any purpose other than to treat symptoms from an event of clinical interest of suspected immunologic etiology. The use of physiologic doses of corticosteroids may be approved after consultation with the investigator. If in the interest of safety, the investigator must treat the subject immediately.
- Inhaled or topical steroids, and adrenal replacement steroid doses ≤ 10 mg daily prednisone equivalent, are permitted in the absence of active autoimmune disease.
- Subjects already taking erythropoietin at the time of screening for the study may continue, provided they have been taking it for more than one month at the time study treatment is started. Prophylactic erythropoietin should not be started during screening or the first two weeks of study treatment but may be started thereafter.
- Granulocyte colony stimulating factors should not be used prophylactically during the first two weeks of study treatment. Use of prophylactic colony stimulating factors may be considered thereafter following discussion with the investigator.
- Live vaccines within 30 days prior to the first dose of NCI-4650 and while participating in the study are prohibited. Examples of live vaccines include but are not limited to the following: measles, mumps, rubella, chicken pox, yellow fever, rabies, Bacillus Calmette-Guérin, and typhoid (oral) vaccine. Seasonal influenza vaccines for injection are generally killed virus vaccines and are allowed. However, intranasal influenza vaccines (e.g., FluMist[®]) are live attenuated vaccines, and are prohibited.
- Radiation therapy to a symptomatic solitary lesion or to the brain may be considered on an exceptional case-by-case basis after documented consultation with the investigator. The subject must have clear measurable disease outside the radiated field. Administration of palliative radiation therapy will be considered clinical progression.

Subjects who, in the assessment by the investigator, require the use of any of the aforementioned treatments for clinical management should be removed from the trial. Subjects may receive other medications that the investigator deems to be medically necessary.

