As indicated in the Moderna Safety Review Committee Dose Level Approval Form dated 13 July 2018, the Moderna Medical Monitor noted that for the six evaluable patients enrolled on Dose Level 2 (Part A) in the Moderna trial (0.13 mg mRNA-4157 monotherapy), no DLTs were experienced and the only AEs experienced were mild, non-serious grade 1 events considered to be related to the experimental treatment. Additionally, as indicated in the Moderna Safety Review Committee Dose Level Approval Form dated 07 September 2018, four evaluable patients were enrolled on Dose Level 2 (Part B) in the Moderna trial (0.13 mg mRNA-4157 in combination with pembrolizumab). These four patients experienced only mild, non-serious grade 1 events considered to be related to the experimental treatment, and no DLTs were seen. The following table shows all grade 1 events experienced by all patients enrolled on Dose Level 2 in the Moderna trial, for both parts A and B:

Adverse Events	Incidence	# of Patients
Injection site (edema, erythema, tenderness)	8	3
Diarrhea	2	1
Photosensitivity	1	1
Arthritis	4	3
Finger edema	1	1
Myalgias	4	3
Flu-like symptoms	1	1

For this trial, because Dose Level 2 has been shown to be safe and tolerated, we propose to enroll our third patient (previously anticipated to be the third patient in Dose Level 2) as the first patient in Dose Level 3. The protocol will enroll three patients at Dose Level 3 unless a patient experiences a DLT.

In each dose level, if a patient experiences a DLT, a total of six patients will be treated at that dose to confirm that no greater than 1/6 patients have a DLT prior to proceeding to the next higher dose level. If a level with 2 or more DLTs in 3-6 patients has been identified, patients will be accrued at the next-lowest dose level, for a total of 6 patients. If two DLTs occur in the second dose level (0.13 mg), the dose will be de-escalated to Dose Level 1 (0.04 mg). If two DLTs occur at Dose Level 1, the study will be temporarily halted, as described in Section **3.2**.

The MTD is the highest dose at which ≤ 1 of 6 patients experienced a DLT or the highest dose level studied if DLTs are not observed at any of the dose levels.

Although the MTD may be reached during this clinical study, determining the MTD is not the aim of the study as benefit from this therapeutic vaccine approach may be achieved at lower doses.

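### Section 4 lifts its bar on prophylactic growth factors one week before the DLT period ends, and the removal wording reaches treatments that Section 4 permits; both are small and cheap to correct

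*Combined protocol and SAP*

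**What the plan says.** On growth factors, Section 4 states: "Granulocyte colony stimulating factors should not be used prophylactically during the first two weeks of study treatment". It continues: "Use of prophylactic colony stimulating factors may be considered thereafter following discussion with the investigator". The red-cell bullet has the same time limit: "Prophylactic erythropoietin should not be started during screening or the first two weeks of study treatment but may be started thereafter". Section 4 also says: "Blood transfusions are allowed at any time during the study, except to meet eligibility criteria".

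Section 3.1.4 sets a longer period for toxicity. DLT evaluation "will occur during the 21 days after the first vaccination for each patient". A DLT is any vaccine-related toxicity of grade 3 or higher, apart from a short list of exceptions. The only laboratory exception is for metabolic abnormalities.

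On removal, Section 4 closes by saying that subjects who, in the investigator's view, "require the use of any of the aforementioned treatments for clinical management should be removed from the trial". Section 3.8.2 lists a matching off-study criterion: "Patients who require the use of any medications listed in Section 4 for clinical management". It adds that nothing further may be collected under this protocol once a subject is off study.

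**The concern.** The plan restricts prophylactic growth-factor support early in treatment, but the restriction ends before the toxicity count does. In the last week of that count, G-CSF given as prophylaxis could keep a falling neutrophil count out of grade 3, and the patient would be scored as having no DLT. Recording the drug, or recording the abnormality as an adverse event under Section 6.1, would not restore the DLT.

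The count is small and carries weight. Section 3.1.5 sets the maximum tolerated dose (MTD) from three to six patients per level, Section 3.1.7 carries that dose into Phase II, and the Phase II halt in Section 3.2 uses the same DLT definition.

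The removal wording is a second, separate problem. Section 4 permits several treatments under conditions, and the two removal statements do not distinguish these from the prohibited ones. A patient who needs a permitted treatment could be taken off study and lost to data collection.

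**Working it through.** The plan gives no figure on this point to reproduce. The check compares the periods and rules.

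**1. The two periods.** Take the two-week bar as Days 0-14 and the DLT period as running to Day 21. The difference is 21 − 14 = 7 days (Days 15-21), or 7/21 = one third of the DLT period. Dose 2 is nominally on Day 14, so these are the days after the second dose.

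**2. Whether neutropenia can be a DLT.** Section 3.1.4 excepts grade 3 fever, pruritus and fatigue; metabolic laboratory abnormalities without significant clinical sequelae and autoimmune toxicity, each if it falls to grade 2 or less within 7 days; and events clearly due to the disease. A related grade 3 neutropenia is outside this list unless it is classed as autoimmune and resolves in that time. A count held at grade 2 is not a DLT.

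**3. What one masked DLT would change.**
- Dose Level 3: "The protocol will enroll three patients at Dose Level 3 unless a patient experiences a DLT". One masked DLT turns 1/3 (expand to 6) into 0/3 (stop at 3). With six patients, it could turn 2/6 (too toxic) into 1/6 (acceptable).
- Phase II halt: 1/5 = 20% triggers it and 0/5 does not. With 6-10 patients two DLTs are needed (1/6 = 16.7%; 2/10 = 20%).
- Conditional illustration only: suppose a Level 3 DLT has occurred and been masked, giving 0/3. The chance that the three patients not enrolled would have shown another is 1 − (1 − p)³. For assumed true DLT rates p of 10%, 20% and 30% this is 1 − 0.729 = 27%, 1 − 0.512 = 49% and 1 − 0.343 = 66%. These figures say nothing about how often masking would happen.

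**4. How likely the event is.** The documents give no rate for neutropenia or for G-CSF use. What they do give points to a rare event:
- Section 4 prohibits systemic antineoplastic therapy on study.
- Section 2.1.1.9 requires an unsupported neutrophil count above 1000/mm³ at entry.
- Section 1.2.9 says hematological effects generally seen with approved intramuscular vaccines have been mild and usually reversible.
- Section 1.2.4 reports that neutrophils rose in the rat study.
- Section 3.1.5 reports no DLT in 3 patients at Level 1 and 6 + 4 at Level 2 in the manufacturer's trial, or in 2 at Level 2 here: 0 of 3 + 6 + 4 + 2 = 15. The manufacturer's Level 2 adverse-event table lists no cytopenia. None of the 15 was treated at Level 3.

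**5. Whether a neutropenia in Days 15-21 would be seen.** Section 3.5.1 schedules a blood count within 2 days before each dose. Nominally these fall on Days 12-14 and 26-28, so none is in Days 15-21. Using the ±5-day windows, dose 2 may fall on Days 9-19 (11 days). A count after Day 14 is possible if dose 2 is given on Days 15-19 (5 of 11) and certain only on Days 17-19 (3 of 11). Dose 3 can come no earlier than Day 23, so its count can come no earlier than Day 21.

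**6. The removal wording.** The removal statements apply to any listed treatment. Section 4 lists permitted items too: topical steroids, established erythropoietin, prophylactic growth factors after two weeks, and injected influenza vaccine. Under Section 6.1, adverse-event follow-up stops when a patient goes off study. Section 3.8.2 names follow-up on the long-term protocol only for patients leaving for progression or study closure.

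**The case against.** The strongest reply is that nobody plausible would receive this prophylaxis: patients are on no chemotherapy and the product raised neutrophils in rats. G-CSF given to a patient already at grade 2 is arguably treatment of an established cytopenia, which Section 4 leaves to the investigator before and after the change. Asymptomatic neutropenia in Days 15-21 would mostly go unseen in any case, for want of a scheduled count. All medications are recorded, and Section 7.6.1 has the team review each patient weekly. Section 3.1.5 also says that finding the MTD is not the aim. These points stand and keep the matter small. They do not give a reason for the bar to end before the count it could protect.

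It can also be said that the removal wording is consistent with the permissions: optional prophylaxis may be considered, while a patient who requires the drug leaves. That reading is available for growth factors. It does not cure the breadth of Section 3.8.2, which refers to any medication listed in Section 4.

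A reader might infer that the two-week bar was written to protect the DLT count and was set wrongly. The documents state no purpose for it, and two weeks also matches the 14-day cycle in Section 3.1.6.

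**Conclusion.** The mismatch is real on the text: seven days of the DLT period are open to prophylactic support that is barred before them. The over-wide removal wording is also real. The expected effect on the MTD or the Phase II halt is very small.

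A reader might infer from the 27%, 49% and 66% figures that the dose selection is materially at risk. The documents do not support that. The figures apply only after a Level 3 DLT has been masked, the DLT rates are assumed, and nothing suggests that the preceding event is other than rare. Nor can it be said that aligning the periods protects an anemia DLT, because transfusion is allowed at any time on study; the erythropoietin change is for consistency.

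The conclusion assumes that the two weeks run from the first vaccination and that Section 3.1.4 is applied as written. It is a wording improvement to consider and does not invalidate the design.

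**What to change.** - In both Section 4 bullets (G-CSF and newly started erythropoietin), replace the two-week limit with the 21-day DLT evaluation period. Keep the bar on starting erythropoietin during screening.
- In the closing paragraph of Section 4 and the matching criterion in Section 3.8.2, limit removal to the treatments and uses that Section 4 prohibits. Patients given palliative radiation would still leave, because Section 4 counts it as clinical progression.

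The cost is one phrase in two bullets and one clause in two places. Prophylaxis is restricted for one more week, and a few patients on permitted support stay on study, in Phase II as well. Treatment of an established cytopenia stays at the investigator's discretion. Sample size, dose levels, the two-stage boundaries and the visit schedule do not change.

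The change does not address transfusion, erythropoietin already established at screening, or the timing of blood counts. How a patient who leaves before Day 21 counts in the 3+3 is a separate question with its own cost, since each replacement needs a new personalized vaccine; it is not part of this fix.
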